Although the recommendations are based on available and mounting evidence of the efficacy of these multidisciplinary interventions (8) Stage 3 program is practically challenging to deliver within KKH paediatric and adolescent weight management clinic (WMC). KKH WMC is currently a physician-led multidisciplinary clinic, which receives the majority of referral from intra-hospital department. There is a wide spectrum of patients being referred to the weight management clinic from low to high-risk obesity. Unfortunately this is taxing on the service that should be servicing mainly the high-risk patients with obesity. The challenges facing WMC are multifactorial

with patient, provider, institutional, and community barriers that affect the achievement of successful outcomes. A few barriers that we are hoping to reduce through our waitlist intervention, are as listed below. One significant institutional barrier is the high manpower resource required to run the Stage 3 multidisciplinary programme. There is also a high rate of patient attrition from stage 3 weight-management clinics and programs (2) Within WMC, our audit shows high level of dropout of 58% after the initial visit (10). KKH WMC receives the majority of referral from intra-hospital department with adolescents ranging from overweight to severely obese with or without comorbidities. However, there is difficulty in moving the overweight adolescents without comorbidities to primary care, due to a lack of trained primary care provider in management of adolescent obesity for Stage 1 program. There is also a lack of structured community services to provide regular contact for adolescents with obesity as required in Stage 1 program as well as the lack of triaged referral pathways for poor responders to primary care intervention.

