The investigator will determine the eligibility of the patients. If the patient is found to be eligible and willing to participate, written consent to participate in the trial will be taken by the nurse coordinator or the clinical research coordinator. The patient's weight and height, body fat composition, waist circumference and blood pressure will be measured as per usual standard protocol or by the study team members and Co-I. Questionnaires to assess eating, quality of life and dietary recall will be administered as part of the research. Accelerometers are optional for patients and will be fitted to assess physical activity. The purpose and instructions for use of activity monitor will be explained, with a copy of the guidelines / instructions provided to all participants. During the measurement period, they will be required to complete an activity diary, providing information on activities / exercises engaged in during the measurement period. In the event the device is removed, they will be required to provide details (e.g, reason and duration) in the activity diary. As the participants will be required to wear the activity monitor throughout the day, including during school activities, a letter to the school / teacher will be provided to explain the reason for wearing the device during the study period. Participants will need to complete a 3-day food diary.

Visit 1 (preferably before visit 2):

Metabolic blood tests (HbA1C, fasting lipid panel, oral glucose tolerance test, fasting insulin level and liver function test) were collected after a minimum 8 hour fasting period together with bloods for AAA, BCAA, long chain acylcarnitines and **vitamin D level, calcium, magnesium, phosphate and alkaline phosphatase** and are optional for participants. Participants may choose to return the accelerometer and food diary during this visit.

Telephone call (before visit 2):

Phone call reminders of the upcoming visit will be provided by the study team member.

Visit 2 (preferably between 4-11 weeks):

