study team members to assess physical activity. If patients do not turn up for the visit, the clinical research coordinator will call the patient to administer the questionnaire and the food diary and obtain a self report height and weight. The clinical research coordinator will attempt up to 3 times to contact the patient. It will be considered a loss of follow up for that visit if patient returns for visit after the window period of 12-23 weeks.

Visit 4: (week 24-36)

Metabolic blood tests (HbA1C, fasting lipid panel, oral glucose tolerance test, fasting insulin level and liver function test) were collected after a minimum 8 hour fasting period together with bloods for AAA, BCAA and long chain acylcarnitines approximately before visit 5 appointment to aid discussion with the doctor during WMC appointment. **Vitamin D level, calcium, magnesium,phosphate and alkaline phosphatase may be performed to assess the bone health of the adolescents.** Blood tests are optional for patients. Accelerometers may also be fitted or returned to study team members to assess physical activity.

Visit 5: (week 24-36)

The follow up will be timed together with the WMC appointment to measure the patient's weight and height, body fat composition, waist circumference and blood pressure as well as administration of the questionnaire. Accelerometers may also be fitted or returned to study team members to assess physical activity. If patients do not turn up for the visit, the clinical research coordinator will call the patient to administer the questionnaire and the food diary and obtain a self report height and weight. The clinical research coordinator will attempt up to 3 times to contact the patient. It will be considered a loss of follow up if patient returns for visit after the window period of 24-36 weeks.

Anthropometric measurement and blood pressure will be measured by trained staff at each clinic visit. The height and weight were measured to the nearest 0.1 cm via a stadiometer (Seca, Model 220; Germany) and 0.1kg via a medical weighing scale (Tanita HD-316, Tanita Corp.; Tokyo, Japan) respectively without shoes and in light clothing. Blood pressure was measured via an electronic sphygmomanometer (Dinamap model 8101, Critikon Inc.; Florida, USA). Waist circumference is measured at the narrowest point between the lower costal (rib) border and the iliac crest using a nonextensible steel tape.

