Physical activity will be assessed using the wGT3X+Actigraph accelerometer. Participants were fitted with an Actigraph, which was worn for 7 days. The monitor was placed centrally on the hip and were set to record acceleration and movement frequency at 5-s epochs, the shortest epoch allowing for seven consecutive days of continuous measurement. The volunteers were asked to wear the monitors during waking hours and to remove them while bathing, showering, and swimming. The Actigraph data were processed using the Actilife 6 software. All days consisting of over 500 min of valid data were included in the analysis. Published thresholds (39) were used to estimate the time spent in different activity intensities. Sedentary activity was classed as <100 counts per minute (cpm) and light intensity activity as between 100 and 1,951 cpm. A threshold of 1,952 cpm was used to estimate time spent in moderate-to-vigorous PA (MVPA). Accelerometer will be provided at suitable timing for the participant to wear for 1 week, preferably during baseline, before or after visit 3, before or after visit 5. If there were any technical glitch, patient can choose to re-wear the accelerometer.

Visit 0: Recruitment, three day food diary, questionnaire and measurement and use of accelerometer

Visit 1(preferably before visit 2): Taking of fasting bloods

Week 1-12: 12 weekly sessions of Kurbo online coaching

Phone call 1 (Week 4): Nurse clinician call to follow up on Kurbo Program progress

Visit 2 (preferably between Weeks 4-11): Doctor's visit for weight management clinic and Measurements

Visit 3 (week 12-23): Measurements, three day food diary, questionnaires and Doctor's visit for weight management clinic and use of accelerometer

Visit 4 (week 24-36): Taking of fasting bloods and use of accelerometer

Visit 5 (week 24-36): Measurements, three day food diary, questionnaires, Doctor's visit for weight management clinic and return of accelerometer

Clinical Research Coordinator may provide timely reminder for patient's visits.

Subjects who miss any visits/ anthropometric measurements/ food diary/ questionnaires/ blood-taking/ recording of physical activity with accelerometer will be excluded from data analysis for that assessment and as long as patient returns for 2 out of 5 visits, it will not be considered as protocol deviation.

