8.2. Statistical and Analytical Plans

Data will be analysed using SAS version 9.3 for Windows (SAS, Inc., Cary, NC USA). BMI will be calculated as kg/m² and BMI-z score calculated using the L, M, S parameters published by the CDC. (34) Baseline demographic, anthropometric measurements, parental BMI, quality of life measurement, disordered eating and physical activity were compared between those in low risk WMC versus those in high risk WMC using the Wilcoxon rank-sum test and the two-sample-t-test for non-normal and normal continuous variables, respectively, and the Fisher's exact test for categorical variables. Changes in cardiometabolic risk factors between first visit and at month 12 will be compared using the paired-sample t-test. Generalized linear mixed model will be carried out on the BMI z-score over multiple visits over 12 month follow up period. The mean value of BMI z-score is considered as a function of time from the baseline. The variance components is used as the covariance structure in generalized linear mixed model. It models a different variance component for each random intercept to allow each child to have his/her own overall level of BMI z-score after taking into account baseline covariate. A time-group interaction will be included to test whether the rate of change of BMI z-score is different between adolescents in low risk and high risk WMC.

There is no reason to assume that this project will lead to an excess of adverse events as the waitlist intervention consists of advice from the nurse and offer of referral to a Kurbo program, neither of which seem likely to create harm. Nonetheless, there are several safety net in place for the waitlist intervention. Firstly, as part of standard Kurbo procedures, any excessive weight loss or weight gain will prompt the Kurbo coaches to inform parents to seek help from their GP and the WMC nurse coordinator will be informed if any concerns arise. Secondly, the WMC nurse coordinator will have administrative rights to Kurbo program and will be able to monitor patient's weight data and communication with Kurbo coaches and will highlight any concerns that arise as a result of intervention. There will also be a feedback form (A month 3 evaluation) administered by the clinical research coordinator on the participants' attitudes to the waitlist intervention and to identify any adverse events at the first WMC visit. As this is a pilot study, there will be no interim analyses.

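### Objective 8 rests on children who chose both optional blood draws, and the single planned paired t-test has no check on whether return for the second draw is selective

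*Combined protocol and SAP*

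**What the plan says.** Secondary objective 8 (Section 2) looks at amino acids, acylcarnitines, insulin, two-hour glucose and fasting lipids at baseline and month 6. Section 8.2 analyses them in one sentence: "Changes in cardiometabolic risk factors between first visit and at month 12 will be compared using the paired-sample t-test".

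Section 5 makes both draws voluntary. The Visit 1 bloods come before the clinic visit "and are optional for participants. Participants may choose to return the accelerometer and food diary during this visit". For Visit 4 (week 24-36) it says "Blood tests are optional for patients". A participant who misses an assessment, blood-taking included, "will be excluded from data analysis for that assessment". Missing a blood visit need not be a deviation: "as long as patient returns for 2 out of 5 visits, it will not be considered as protocol deviation".

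The mixed model in Section 8.2 is for BMI z-score only. For the blood results there is no missing-data method, no sensitivity analysis, and no comparison of children with one draw and children with two. The comparison planned in Sections 4.2 and 11.1 is between participants and eligible people who decline the study.

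**The concern.** A paired t-test uses only complete pairs, so a child with one draw contributes nothing. Suppose children with a worse first result are more likely to return. Part of a high first value is chance, so their second values fall on average even if nothing has changed, and the paired mean shows an improvement. If children with better first results return more often, the same mechanism produces a worsening. There is no concurrent untreated group that would expose this, and the plan collects nothing in the analysis that would show whether return was selective.

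At stake is the conclusion on objective 8: a reported 6-month change in insulin, glucose, lipids or metabolites could come partly from who came back. The primary objective (proportion triaged to the low risk clinic) is not affected.

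**Working it through.** The plan states no alpha, power, SD or effect size for this comparison, and Section 8.1 says there is no sample size calculation, so there is no figure of the plan's own to reproduce.

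**Inputs from the documents**
- Planned enrolment 45 (Section 4.1).
- Dropout 58% in the clinic audit and 19% in the earlier Kurbo pilot (both Section 1). Used only as a range: return 42% or 81%.
- Pairs, if all 45 give a first draw: 45 × 0.42 = 18.9 and 45 × 0.81 = 36.5. There are fewer if some decline the first draw.

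**Assumptions**
- Two-sided 5% test, marker SD 1 at both draws, no true change in any child.
- Correlation ρ = 0.5 between draws (0.7 as a variation).
- Log-odds of return rise by 0.5 or 1.0 per SD of the driving variable.

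**1. Return depends on the first result.** For a child with first result b (in SD from the mean), the expected change is −(1 − ρ)b. The bias of the paired mean is therefore (1 − ρ) × (mean first result among returners), with sign opposite to the selection. The mean among returners comes from integrating the logistic return curve over a normal distribution. Type I error is from simulation, and separate runs differ by up to about one percentage point.

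| Return | Log-odds per SD | Mean first result, returners | Bias at ρ = 0.5 | Type I error |
|---|---|---|---|---|
| 42% | 0.5 | 0.274 | 0.5 × 0.274 = 0.14 SD | 9% |
| 42% | 1.0 | 0.481 | 0.5 × 0.481 = 0.24 SD | 17% |
| 81% | 0.5 | 0.092 | 0.5 × 0.092 = 0.05 SD | 5 to 6% |
| 81% | 1.0 | 0.165 | 0.5 × 0.165 = 0.08 SD | about 7% |

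The standard error of the paired mean is about 0.23 SD at 42% return and 0.16 SD at 81%. The worst bias is thus about one standard error in the first case (0.24/0.23) and half of one in the second (0.08/0.16). At ρ = 0.7 and 42% return the bias falls to 0.3 × 0.274 = 0.08 and 0.3 × 0.481 = 0.14 SD.

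An estimate that uses every first draw (second regressed on first, evaluated at the mean of all first draws) has bias 0.00 SD here. Its standard error is 0.22 against 0.23 SD when return is random, and about 0.25 against 0.23 SD at the steepest slope and 42% return, roughly 10% larger.

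**2. Return is random.** The paired test has bias 0.00 SD and type I error 5%. Only precision is lost.

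**3. Return depends on the child's stable level.** Let each result be a stable part plus independent noise, with return driven by the stable part alone. The stable part cancels in the difference, so the paired test has bias 0.00 SD and type I error about 5%. The all-first-draws estimate is now the biased one. At ρ = 0.5, 42% return and slope 0.5, its bias is roughly (1 − 0.5) × √0.5 × 0.274 = 0.10 SD. At slope 1.0 simulation gives 0.18 to 0.19 SD.

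**4. Return depends on the child's own change.** At ρ = 0.6 and odds ratios of 1.5 to 3 per SD of improvement, in SD of change:
- 81% return: paired bias 0.08 to 0.18, all-first-draws bias 0.06 to 0.15.
- 42% return: paired bias 0.23 to 0.51, all-first-draws bias 0.18 to 0.43.

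Neither estimate is safe.

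**The case against.** The strongest reply is that what matters is whether return is related to the child's change, not to the first result as such. If return follows usual severity, the paired difference removes it. That is plausible here, because Section 5 gives the high risk clinic weekly and then two-weekly contact and the low risk clinic two-monthly contact. In that case a mixed model put in place of the paired test would add bias. This stands, and it is why the mixed model should accompany the paired test and not replace it.

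The return rates are also open to challenge. A reader might infer from "our audit shows high level of dropout of 58% after the initial visit" that more than half of the second draws will be lost. The documents do not support that. The figure is past clinic attrition, listed among barriers the intervention is meant to reduce. The Kurbo pilot lost 19%, Section 14 reimburses SGD50 per visit attended in the window, and no uptake rate for the draws is given anywhere.

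A reader might also infer that first results will prompt return, because Section 5 says bloods inform the discussion with the doctor. That remark concerns the second draw and the Visit 5 appointment. That clinicians see the Visit 1 results is a fair inference from their timing before a visit that screens for co-morbidities, but nothing says they influence who returns, or in which direction.

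Finally, this is one secondary objective of an uncontrolled pilot. Time trends, and regression to the mean from how children were referred, remain under either model. True, and it limits the weight of the point without removing it.

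**Conclusion.** The point holds in a conditional form. Objective 8 will be answered from complete pairs of optional draws by one test, with nothing planned to detect selective return. If return depends on the first result, at correlation 0.5 and log-odds of 0.5 to 1.0 per SD, the spurious change is about 0.14 to 0.24 SD with type I error 9 to 17% at 42% return, and 0.05 to 0.08 SD with 5 to 7% at 81% return. The slopes and correlation are assumptions, and the return rates come from other settings.

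Two stronger readings are tempting and go too far. One is that the paired test is invalid as planned, or that its type I error is not 5%: it is unbiased if return is random or follows only the stable level. The other is that a likelihood model using all draws cures the problem: it does so only when return depends on observed data such as the first result. Neither analysis should stand alone.

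Separately, the month 12 in the quoted sentence does not fit the month 6 objective (Section 2), the week 24-36 draw or the six-month participation (Section 5).

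**What to change.** In Section 8.2:
- Keep the paired t-test. Beside it, pre-specify for each marker a linear mixed model with visit as a factor, an unstructured 2×2 covariance, small-sample degrees of freedom and baseline BMI z-score as covariate, including every child with at least one draw.
- Report how many children gave 0, 1 and 2 draws.
- Compare first results and baseline BMI z-score between children who returned for the second draw and those who did not.
- Claim a metabolic change only if the two analyses agree.
- Reconcile month 12 with month 6 in Section 2 and the week 24-36 draw in Section 5.

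The cost is wording and one more model per marker, with no new data and a model class already planned for BMI z-score. The mixed model's standard error may be up to about 10% larger when return depends strongly on the first result. It remains biased if return follows an unobserved stable level (0.10 to 0.19 SD at 42% return) or the child's own change; baseline BMI z-score helps only as far as it captures that level. Agreement between the two analyses is therefore supportive evidence, not proof.

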The app's data driven platform provides users with feedback via push notifications, text messages and emails. Kurbo utilizes Traffic Light Diet (18) to categorise foods into reds, yellows and greens. The Kurbo program teaches users to gradually reduce their consumption of red(high caloric) food over time instead of focusing on caloric counting which promotes disordered eating behaviours (19). The app is supplemented with weekly live coaching with a Kurbo behavioural coach. Coaches check in with the adolescents for 15 minutes once a week via video, phone or text. Health care professionals, who referred their patients, will also have access to the patient's progress through the Kurbo administrator site. Briefly, Kurbo coaching philosophy is based on a theoretical model of human support called Supportive Accountability (20). Human increases adherence through accountability to a coach who is seen as trustworthy, benevolent, and having expertise. Details about Kurbo coaching philosophy, screening, training and supervision of coaches is as attached in Appendix 1. Terms and conditions about Kurbo program is attached in Appendix 2. The program is licensed from the Stanford Packard Pediatric Weight Control Program and is currently part of the weight management program in Stanford and Florida's Children weight management clinic. There are also ongoing trials in Baystate Pediatric weight Management Program and University of Chicago on the utility of Kurbo Program. Locally, Health Promotion Board had conducted a pilot study using Kurbo Program on 80 overweight and obese children aged 8-17 years old as a school-based initiative. The pilot study showed a low drop-out rate of 19%. 65 families completed the 3 month program with a significant drop in BMI z-score by 0.26. Of this group, 90% of the children either maintained or reduced their weight. Of those who reduced their weight, 58% reduced their BMI by over 3% and 20% reduced their BMI by over 7%. Reduction of BMI \bar{z} -score of more than 0.25 has been found to be clinically significant for reduction of cardiovascular risk factors. (21)

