2. HYPOTHESIS AND OBJECTIVES

Primary objective will be to examine the proportion of patients triaged to the low risk WMC clinics after brief intervention by a nurse coordination and completion of 4 sessions of Kurbo Program over a 12 month recruitment period.

Secondary objectives:

1. To examine the effect of the waitlist intervention and WMC intervention on mean BMI z-score change at 3 months and 6 months.
2. To examine the feasibility of using Kurbo program as a waitlist intervention for the target population as measured by quantifying the percentage of patients offered the program who agreed to enrol.
3. To examine program fidelity as measured by the percentage of patients who complete each of the 12 sessions of online coaching by Kurbo coaches
4. To examine changes in treatment outcomes as a function of program fidelity as measured by those who complete more online coaching show greater improvements in BMI z-score
5. To examine other factors that predict poor response (parental BMI, quality of life, disordered eating and physical activity measurement) in high risk WMC
6. To examine the effects of waitlist intervention on lifestyle changes (nutrition and physical activity), quality of life and disordered eating at 3 and 6 months.
7. To examine the rate of attrition from WMC after implementation of the waitlist intervention and new model of care in WMC.
8. Examine changes in branched chain amino acid(BCAA), aromatic amino acid (AAA) and long chain acylcarnitines, insulin and second hour glucose results and fasting lipids at baseline and at month 6.

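### Section 8.2 contains no analysis that estimates the mean BMI z-score change at 3 and 6 months named in secondary objective 1, and its wording leans towards a straight line in time that could understate the 3 month change.

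*Combined protocol and SAP*

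**What the plan says.** Section 2, secondary objective 1, reads: "To examine the effect of the waitlist intervention and WMC intervention on mean BMI z-score change at 3 months and 6 months". These are two means at stated times, for the children who go through the programme as a whole.

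Section 8.2 gives one analysis of BMI z-score: "Generalized linear mixed model will be carried out on the BMI z-score over multiple visits over 12 month follow up period". On time it says "The mean value of BMI z-score is considered as a function of time from the baseline". Each child has a random intercept, after allowance for an undefined baseline covariate. The only stated inference is the interaction, which is to "test whether the rate of change of BMI z-score is different between adolescents in low risk and high risk WMC". The paired t-test in the same section is for cardiometabolic risk factors at month 12, not for BMI z-score.

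Section 5 schedules anthropometry at baseline, Visit 2 (weeks 4-11), Visit 3 (weeks 12-23) and Visit 5 (weeks 24-36). The schedule lists "Week 1-12: 12 weekly sessions of Kurbo online coaching". Placement in the low or high risk clinic comes after baseline and depends partly on the change in BMI percentile over the first four coaching sessions.

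Section 1 reports a local school-based pilot, in which 65 families completed 3 months "with a significant drop in BMI z-score by 0.26". It also cites a fall of more than 0.25 as clinically significant.

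**The concern.** Followed as written, section 8.2 yields a test of whether two clinics differ in rate of change. It does not yield the two numbers that objective 1 asks for. With the interaction in the model, the time coefficient belongs to the reference clinic. A cohort figure would need a weighting of the two clinics that the plan does not give. The grouping is also partly a result of the outcome, because early BMI change helps decide the clinic.

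The form of the time effect is open as well. Speaking of a single rate of change per clinic suggests a straight line. Weekly coaching is scheduled only to week 12, and clinic contact also changes in frequency over time, so a constant slope over weeks 0-36 does not follow from the design. A straight line through baseline cannot show a plateau or regain, which is the main reason to ask for 3 and 6 months separately. If the form is left open, it can also be chosen after the data are seen.

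**Working it through.** **No plan figure to reproduce.** Section 8.2 gives no expected change, SD or within-child correlation for BMI z-score, and no document gives a path after 3 months. The -0.26 is the pilot result in section 1, used here only as an example. Visit times come from section 5. The paths after week 12 and the residual SD are assumptions.

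**1. Straight line, baseline as an outcome.** With common visit times and complete data, the time slope of a random-intercept model is the least-squares slope through the mean path, b = Sxy / Sxx. The reported change at time t is b × t, so the change at 6 months is always twice that at 3 months.

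Take visits at weeks 0, 6, 14 and 30, with linear loss to -0.26 at week 12 and then a plateau. The true means are 0, -0.13, -0.26, -0.26.
- Mean time = 50/4 = 12.5; deviations -12.5, -6.5, 1.5, 17.5.
- Sxx = 156.25 + 42.25 + 2.25 + 306.25 = 507.
- Sxy = (-6.5)(-0.13) + (1.5)(-0.26) + (17.5)(-0.26) = 0.845 - 0.39 - 4.55 = -4.095.
- b = -4.095/507 = -0.00808 per week.
- Reported change: 14b = -0.113 and 30b = -0.242; the truth is -0.26 at both.

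**2. Dependence on the assumed path.** Take visits at months 0, 1, 3 and 6, with linear loss to -0.26 at month 3 and a value y6 at month 6. The deviations are -2.5, -1.5, 0.5, 3.5 and Sxx = 21. The month 1 and month 3 terms cancel: (-1.5)(-0.0867) + (0.5)(-0.26) = 0. So b = 3.5·y6/21 = y6/6, and the reported 3 month change is y6/2, whatever happened at 3 months.

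| Assumed path after month 3 | y6 | Reported 3 month change (truth -0.26) |
|---|---|---|
| Loss continues at the same rate | -0.52 | -0.26 |
| Loss slows (1.5 times the 3 month value) | -0.39 | -0.195 |
| Plateau | -0.26 | -0.13 |
| A quarter regained | -0.195 | -0.098 |
| Half regained | -0.13 | -0.065 |
| All regained | 0 | 0.00 |

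**3. Visits spread over the protocol windows.** 2000 simulated trials of 45 children, visit times uniform within each window, assumed residual SD 0.12, plateau path:
- Straight line: -0.105 at week 13 and -0.21 at week 26 (truth -0.26 at both). The week 13 95% interval covered the truth in 0 of 2000 trials.
- Slope change at week 12: -0.261 at both times. This path has its bend exactly at the knot, so the result favours that model.
- Standard error at week 13: about 0.011 for the line and 0.027 for the knot model. At week 26 they are about equal (0.023 and 0.022).

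**4. Straight line, baseline as a covariate.** If only Visits 2, 3 and 5 are outcomes, the line need not start at zero. At weeks 6, 14 and 30 the changes are -0.13, -0.26, -0.26.
- Mean time 16.67, mean change -0.2167, Sxx = 298.67, Sxy = -1.387, b = -0.00464.
- Fitted change at week 14: -0.2167 + (-0.00464)(14 - 16.67) = -0.204.
- Over the protocol windows the simulated values are -0.206 at week 13 and about -0.26 at week 26.

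**5. Visit as a categorical factor.** Simulation with fixed visits at months 0, 1, 3 and 6 returned the 3 month change (about -0.26) under every path tried. It also returned the 6 month change: about -0.26 for the plateau, -0.13 for half regain and -0.52 for steady loss.

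**The case against.** The strongest reply is that linear time is never stated. A model in which the mean depends on time, fitted over multiple visits, is compatible with visit as a factor, and that model would give both changes without this bias. This stands: the plan leans towards a line but does not commit to one, so the bias is conditional.

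The size is conditional too. The -0.26 comes from completers of a different programme setting, no path after week 12 is assumed anywhere, and steady loss gives no bias. Clinic care begins around Visit 2 and continues beyond week 12, so a bend exactly at week 12 is not established. Reading the baseline covariate as baseline BMI z-score removes most of the 3 month bias under the plateau. All of this stands, and it is why the figure must be given as a range.

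A cohort mean could be derived from the interaction model as a weighted contrast. That is true, but the plan specifies neither the contrast nor the weights.

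A reader might infer three stronger things that the documents do not support:
- That the plan will report a true -0.26 as -0.11. This needs linear time, baseline as an outcome and a plateau, none of which is stated.
- That children lost before Visit 2 fall out of the model for want of a clinic. Section 5 places those who do not sign up for the coaching in the high risk clinic, so many could have a group value.
- That the 0.25 benchmark decides the trial's result. It is background in section 1, and the primary objective is the proportion triaged to the low risk clinic.

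**Conclusion.** The mismatch between objective and analysis holds on the text alone: objective 1 asks for cohort mean changes at 3 and 6 months, and section 8.2 specifies neither. No assumption about trajectories is needed for that.

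The bias is a conditional consequence. With linear time and baseline as an outcome, any slowing, plateau or regain after the coaching period pulls the 3 month estimate towards no effect. Under a plateau after a true -0.26, the report would be about -0.11 with visits in the protocol windows. Across the assumed paths it runs from about 0 (full regain) to -0.26 (steady loss). With baseline as a covariate the plateau figure is about -0.21.

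This is a cheap improvement of moderate severity. It concerns a secondary objective of a pilot with no sample size calculation, and does not touch the primary objective.

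**What to change.** In section 8.2, add a separate model for objective 1:
- Include all enrolled children, without the clinic term or its interaction.
- Take visit (baseline, 2, 3, 5) as a categorical factor, with a random intercept per child. As an alternative, use actual week with a change of slope at about week 12.
- Report the model-based mean change from baseline at 3 and 6 months with 95% confidence intervals.
- State whether baseline BMI z-score is an outcome or a covariate.
- Keep the low versus high risk contrast as a separate secondary model, and note that the grouping partly reflects early BMI change.
- Reconcile the 12 month analysis period in section 8.2 with the 6 month participation in section 5.

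The cost is SAP wording and one or two model terms, on data already scheduled. The price is precision at 3 months. Under the assumed residual SD of 0.12, the week 13 standard error rises from about 0.011 to 0.027 with the knot model, so the 95% half-width goes from 1.96 × 0.011 = 0.022 to 1.96 × 0.027 = 0.053; at week 26 there is almost no loss. The two options differ: categorical visit assumes no shape but averages over wide windows (weeks 12-23 and 24-36), while the knot model targets an exact week but assumes where the bend lies. The choice should be fixed before the data are analysed.
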